4.4. Educational sessions (arm 2 & 3)

Participants included will attend an information session. The information session will take place in the space where the group activities take place (provided by the organizations), the classroom of the integration course or a private room nearby the social restaurants. Sessions will be organized following the group activities (e.g. after sport activity, integration course or meal in social restaurant), with an approximate duration of 20 minutes (excluding sample taking). The sessions will be organized both during weekdays and weekends, depending on the activities they are linked to and according to the preferences of the organizations and women. The content of the session will cover sexual health, cervical cancer and screening services off-site. In the last part of the information session, participants in:

- **arm 2** - will be provided information on how to be screened for cervical cancer and where they can obtain these services off-site.
- **arm 3** - will be provided information on how to be screened for cervical cancer, and where they can obtain these services off-site. In addition, they will receive information on self-sampling and will be offered a self-sampling kit and asked to take a sample on-site and return it.

4.5. Cervical cancer screening through self-sampling (arm 3)

4.5.1. Self-collection

Women in arm 3 will receive information regarding the self-sampling test and they will be invited to collect a self-sample at the same moment. Contact information (i.e. a telephone number) will be collected in order to inform the women about their test result in case they test positive for HPV.

Each kit will include a self-sampling device (i. e. The Evalyn Brush (Rovers, The Netherlands)), an instruction leaflet and a recipient to store the sample. The self-sample can be taken on-site - after the information session -, in a private, comfortable and safe space where it is comfortable for them to do so.

All the samples collected will be returned to the researcher. The researcher will then directly label the samples (cfr section 4.5.2).

4.5.2. Sample management and storage

Samples will be collected, the Evalyn brush will be rinsed in a recipient filled with preservative medium (i.e. ThinPrep or Roch Cell Collection medium) and the recipient will be labelled using a unique identification code corresponding to the participant and labelled using a unique identification code corresponding to the participant. Also, the date, location of collection and study country will be added. Before analysis and after homogenization, the sample will be divided in 2: 1 part of the sample will be used for the HPV analysis, the second half will be stored to be used in other components of the study (e.g. during the validation phase of the cartridges of the new ELEVATE screening tool) and/or for future research regarding sexual and reproductive health.

Each of the samples will be labeled with a unique identifier code that will be composed out of 21 digits:

X-X-XX.XX.XXXX-XXX-XX.XX.XXXX

- The 1st referring to the country it was collected:
 - 1: Belgium
 - 2: Brazil
 - 3: Ecuador
 - 4: Portugal
- The 2nd referring to the health/community centre where it was collected: all centres/organizations that will collaborate will be given 1-digit number
- 8 digits referring to the birth date of the patient: dd-mm-yyyy
- 3 digits referring to the number of included/sampled patients, starting in each centre with 001.
- 8 digits referring to the day of sample taking

We will color-mark the label to make clear which sample will go for HPV-analysis and which will be stored.

This unique identifier code will also be used to link the samples with the socio-demographic information of the woman (see section 5.2.2) and to ensure pseudonymization of the data and samples (see section 7).

Besides mentioning the code, the label of the sample should also state the HPV status (once the result is known).

After the end of the study (December 2023), the samples will be stored up to 5 years, only and if only the participant has given permission to use her samples in future research. Other samples will be destroyed.

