A questionnaire will be applied during a follow-up phone call 3 months after the session to assess whether or not a screening appointment was made and participants got screened (=uptake), as well as to evaluate

knowledge after receiving the informative session (*Obj 2, Obj 4 and Obj 5*). (See Appendix IV: questionnaire 4)

Knowledge and willingness to get screened will be assessed by applying short, closed questions in order to quickly evaluate these outcomes by phone.

Women will be contacted through a message, phone call or e-mail (according to their preference) asking them when would be convenient for them to answer some questions. Women will be contacted up to 5 times maximum before considering them lost-to-follow.

Each participant will be attributed a unique identifier alpha-numeric code that will be used to link the respective questionnaires and to ensure pseudonymization of the data. The information that links the unique identifier code to the name and contacts of the participants will be registered. Only the community-based researcher (healthcare professional or community health worker) responsible for the data collection will have access to these personal data. No other member of the research team will have access to the name and contacts of the participants.

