9.4. General consent statement

A written consent form will be asked of all participants, in full compliance with the Declaration of Helsinki. The consent form will be written in simple language at a sixth-grade reading level. The language used in the consent form will be developed in collaboration with medical staff accustomed to share medical information with their patients.

The form will clearly state the objectives of the study and will also include a small screening section that will be used to verify whether or not the approached woman is eligible. When a woman is considered eligible, she will be explained in more detail what is expected from her, i.e. which procedures will take place if she decides to participate.

Only participants with decision-making capacity, that is, they are able to give consent, will be involved in the research. Language and literacy capabilities will be assessed. In case the participant cannot read or write herself, an impartial witness will be asked to join the reading of the consent form (authorized substitute decision maker). The witness will sign the consent form together with the participant. The participant will choose a witness so she can select someone she believes is appropriate and reliable (e.g. another woman from the community – without conflict of interest).

The following topics will be covered in the information sheet of the informed consent:

- Description of the study and its objectives
- To know that participation is voluntary
- To be able to withdraw themselves, their samples and their data from the project at any time
- To know that results can be shared with the participants
- Benefits and risks
- No costs for participants
- To receive assurances that appropriate insurance coverage is in place
- To have confidentiality and privacy protections clearly specified, following national legislations.
- To know of any potential commercial exploitation of the research.
- To know that students might participate in this study as research assistants.

Women will be asked if their data can be used in future research. If they agree, they will be asked to tick the box 'I consent to have my data deposited in pseudonymised form in a trusted repository so it can be used for scientific purposes only'. If they don't tick the box, their data will not be released for further use in other research.

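### The 21-digit sample code carries full birth date, centre and sampling date beside HPV status, so it does not deliver the stated pseudonymisation, and its relation to the alpha-numeric participant code is unresolved

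*Protocol*

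**What the plan says.** Protocol section 4.5.2 states: "Each of the samples will be labeled with a unique identifier code that will be composed out of 21 digits". The template is "X-X-XX.XX.XXXX-XXX-XX.XX.XXXX": one digit for country, one for centre, then "8 digits referring to the birth date of the patient: dd-mm-yyyy", three digits for a running number that starts at 001 in each centre, and "8 digits referring to the day of sample taking". The code is to link the sample to the questionnaire data of section 5.2.2 and "to ensure pseudonymization of the data and samples (see section 7"). Once known, the HPV result goes on the same label (4.5.2, 4.5.3). One half of each sample is sent to Ghent University, and with the woman's permission samples may be kept for up to five years after the study.

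On timing, section 4.5.1 says: "All the samples collected will be returned to the researcher. The researcher will then directly label the samples". The kit it lists is a brush, a leaflet and a recipient.

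Section 5.2.2.4 describes an identifier for everyone: "Each participant will be attributed a unique identifier alpha-numeric code that will be used to link the respective questionnaires". Its structure is not given. The file joining it to names and contact details is open only to the data collector (5.2.2.4, 9.3). Section 7 speaks of a single unique identifier code that links all of a participant's questionnaires.

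**The concern.** Pseudonymisation means that a record cannot be traced to a person without additional information that is held apart. The protocol places that protection in the restricted link file. A code that shows the birth date bypasses the file for any reader who already knows that date. The information exposed is HPV status, in a study that plans a stigma reduction programme (9.1).

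The second issue is record linkage. Objective 5 asks whether HPV-positive women go on to follow-up testing and care. That needs the laboratory result, filed under the sample code, joined to the three-month questionnaire, filed under the participant code. If the two identifiers have no defined relation, the join depends on local improvisation in four countries.

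**Working it through.** **1. Code length.** Fields in section 4.5.2: 1 (country) + 1 (centre) + 8 (birth date) + 3 (running number) + 8 (sampling date) = 21. The template also has 21 positions, so the stated length reproduces.

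**2. How much of the code is needed.** Dates take 8 + 8 = 16 digits. Without the birth date, 21 − 8 = 13 remain; without either date, 21 − 16 = 5 remain (country, centre, running number). Because the running number starts at 001 within each centre, those 5 digits already separate all sampled women. The dates add personal content and no uniqueness.

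**3. How far a known birth date singles out a label.** Inputs: ages 25 to 65 (section 4.2.1), so D = 40 × 365.25 = 14,610 possible birth dates, or 41 × 365.25 ≈ 14,975 if age 65 is counted in full. Assumptions: uniform birth dates, and n women per centre. The protocol gives no centre size, so a range is shown. The chance that no other woman in the centre shares a given woman's birth date is (1 − 1/D)^(n−1):

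| n per centre | D = 14,610 | D ≈ 14,975 |
|---|---|---|
| 20 | 99.9% | 99.9% |
| 100 | 99.3% | 99.3% |
| 500 | 96.6% | 96.7% |
| 999 (limit of three digits) | 93.4% | 93.6% |

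These figures are conditional: they apply to a reader who can see the labels or data and knows the woman's birth date and centre. They are not the probability that a woman will be re-identified.

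**4. Who could be such a reader.** Sections 7 and 9.3 open the pseudonymised data to the research team and the community-based researchers. Section 4.2.2 aims to include in each session team someone from the host organisation, who may know the women professionally. Section 9.3 withholds names and contact details from the wider team but does not address birth dates carried in the code.

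**5. One code or two.** Section 4.5.2 refers to section 7, where one code links all questionnaires. Section 5.2.2.4 gives an alpha-numeric code to each participant. The 4.5.2 code is all digits.

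- *If one code is meant:* it ends in a sampling date, so it cannot be completed for arm 2 women or for arm 3 women who decline. In arm 3 it is incomplete until sampling, although the first questionnaire is filled in at the start of the session (5.2.2.1).
- *If two codes are meant:* every participant has an identifier, but the protocol does not say how the sample code maps to the participant code, and Objective 5 needs that mapping.

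**6. Labelling.** The kit in 4.5.1 lists no code, and labelling follows return. No code is described on the sample between collection and return, and no check at hand-over is described. Under section 4.5.4 women with negative results get no results call, so an error in this interval could go unnoticed.

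**The case against.** The best defence is that the code holds no name or contact detail, that access is limited to the study team (7, 9.1, 9.3), and that section 9.3 promises a separate data-security document that is not shown here. It is also true that the primary endpoint is participation in screening (6.1), so no effect estimate is biased. All of this stands. It limits the point to re-identifiability and linkage, but it does not supply the property that section 4.5.2 claims for the code.

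A reader might infer more than the text supports:

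- *That returned samples stay unlabelled.* Section 4.5.1 has the researcher label them directly on return. Only the interval before that is uncovered, and nothing in the text shows that mix-ups will occur.
- *That arm 2 women and refusers have no identifier.* The 21-digit code is defined for samples, and 5.2.2.4 gives every participant a code. The difficulty arises only if the two are meant to be the same.
- *That nothing connects the codes.* Section 4.5.2 says the sample code links to the questionnaire data. The intention is stated; the mechanism is not.
- *That Objective 3 and Hypothesis 4.4 are also at risk.* Objective 3 uses attitude and user-experience questionnaires, and Hypothesis 4.4 compares women who refuse sampling with arm 2. Neither needs an HPV result.
- *That the code goes into a public deposit.* The consent wording is "my data deposited in pseudonymised form in a trusted repository"; it does not say that this code accompanies the data.
- *That anyone at a host organisation could identify a woman.* The access rules do not support this. The reader needs access to labels or data as well as the birth date.

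**Conclusion.** The point holds in two parts. First, the sample code makes women re-identifiable without the link file, because it shows full birth date, centre and sampling date beside HPV status. Sixteen of its 21 digits are dates that uniqueness does not require. Under uniform birth dates and assumed centre sizes of 20 to 999, a known birth date would single out a woman's label within her centre about 99.9% to 93.4% of the time. Second, sections 4.5.2, 5.2.2.4 and 7 do not settle whether there is one identifier or two, and each reading leaves a gap. The consequences are for confidentiality and for the linkage behind Objective 5, not for the primary comparison. Both parts rest on the wording of the protocol alone; only the percentages depend on assumptions. The change is worth making before labels are printed.

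**What to change.** Replace both identifiers with one study ID without personal content: country, centre, a sequential or random number, and a check digit. Assign it at consent to every participant in arms 2 and 3, and use it on all questionnaires and samples. Hold birth date and sampling date as separate restricted fields. Put the ID on the kit recipient before it is handed over, and check it against the participant on return. Amend sections 4.5.1, 4.5.2, 5.2.2.4 and 7 so that they name the same identifier.

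The cost is a revised label template, the matching text changes, and a few unused labels for women who decline sampling.

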4.5.3. Sample analysis

One half of the sample will be analysed in each study country. Analysis is expected to take a maximum of 2 weeks. After the result is known, the HPV status will be indicated on the sample.

The other half of the sample will be send to Ghent University, Belgium, and stored for further use in other components of the study (e.g. the validation of the cartridges in a later stage of the project) and/or for future research regarding sexual and reproductive health.

4.5.4. Communication of results

Women who tested positive for HPV will receive their result by phone, by email or in a one-on-one counselling with a researcher with medical background or community/social worker who is trained to answer related questions and refer to a physician if the questions are more complex and/or out of the scope of screening. After sample-taking, we will ask the participant how and when she prefers to be contacted. We will already explain to them that they will only receive a phone call in case of a positive test result. If they tested negative for HPV we won't call them to communicate their results (concept of 'no news = good news'). We will only call them 3 months later for the follow-up call.

All women who tested HPV-positive will be guided to a referral centre (by making an appointment for them, giving them directions and coordinates) for follow-up, following the local clinical guidelines.

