4.6. Follow-up of participants

All participants of arm 3 who took the self-sample and tested positive will be contacted by phone 2-3 weeks after their participation to inform them on their test result.

All participants (arm 2 and 3) will be contacted by phone **3 months** after their participation:

- to gauge the **knowledge** on cervical cancer screening after the education session
- to verify whether they got a **pap smear** (all women in arm 2 and HPV-positive women of arm 3)
 - if not, why not
 - was an appointment made?
 - if not, why not

In case women do not have a phone, the community-based researcher can discuss with them the best way to schedule a day or set a temporary 'drop-in centre' for them to come in.

5. Data collection

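### Arm 3 women are told that a call comes only if they are HPV-positive, but no retry rule or enquire-by date is stated for a result contact that fails

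*Protocol*

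**What the plan says.** Protocol section 4.5.4 sets out how results are communicated in arm 3. After sampling, staff ask each woman how and when she wants to be contacted. They also tell her what silence means: "We will already explain to them that they will only receive a phone call in case of a positive test result". The section names the principle, "no news = good news", and says of negative women: "We will only call them 3 months later for the follow-up call". A positive result may be given by phone, by email or in person. Positive women are then guided to a referral centre "by making an appointment for them, giving them directions and coordinates".

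The timing is in two other places. Section 4.5.3 says "Analysis is expected to take a maximum of 2 weeks". Section 4.6 says that all arm 3 women who took the sample and "tested positive will be contacted by phone 2-3 weeks after their participation to inform them on their test result". The next contact, for everyone in arms 2 and 3, is the phone call at 3 months.

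Two provisions deal with women who are difficult to contact. Section 4.6 says: "In case women do not have a phone, the community-based researcher can discuss with them the best way to schedule a day", or a temporary drop-in centre can be set up. Section 5.2.2.4, on the follow-up questionnaire, says: "Women will be contacted up to 5 times maximum before considering them lost-to-follow".

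**The concern.** The message makes silence informative. For a negative woman it is correct. For a positive woman whose number has changed, who does not answer or who does not read an email, it misleads, and she has been given no reason to ask. The wording also mentions only a phone call, although email and face-to-face routes are allowed. A woman who chose email and missed the message has still been told that no call means no positive result.

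Failed contact is foreseeable here. The trial recruits women defined as hard to reach, and the protocol itself plans for women without a phone and for loss to follow-up at 3 months. At stake is delayed follow-up of a positive HPV test. There is also a smaller consequence for Hypothesis 5.1 (that positive women go on to follow-up testing and care): a woman who does not know her result cannot act on it.

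**Working it through.** The protocol gives no figure of its own for this point. The check has two parts.

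**1. Does any provision cover a failed result contact?**

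| Provision | Section | What it covers | Covers a failed result contact? |
|---|---|---|---|
| Telephone number collected to report a positive result | 4.5.1 | Makes contact possible | No; no second contact is mentioned |
| Preferred route and time recorded | 4.5.4 | Makes failure less likely | No; it is agreed beforehand and is not a fallback |
| Appointment made for positive women | 4.5.4 | Helps the woman attend | No; she must first be reached |
| Scheduled day or drop-in centre | 4.6 | Women without a phone | Not stated for a wrong number or an unanswered call |
| Up to 5 attempts by message, phone or email | 5.2.2.4 | The 3-month questionnaire | Not stated for results |
| Emergency and complaint contacts | 9.4 | Emergencies and complaints | Not stated to invite enquiries about a result |
| Patient safety plan | 9.1 | Harms and emergencies | Unknown; the plan is not shown |

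So the protocol sets a retry rule for the questionnaire but states none for a positive result.

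**2. How long could the silence last?**

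Inputs: result contact at 2-3 weeks and next contact at 3 months (both section 4.6).

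Formula: gap = week of the 3-month call − week of the planned result contact.

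- 3 months as a quarter year: 365.25 / 4 / 7 = 13.04 weeks. Gap = 13.04 − 3 = 10.04 to 13.04 − 2 = 11.04 weeks.
- 3 months as 90 days: 90 / 7 = 12.86 weeks. Gap = 9.86 to 10.86 weeks.
- 3 months as 12 weeks: gap = 9 to 10 weeks.

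The gap is therefore about 10-11 weeks, or 9-10 on the shortest reading, provided that no retry succeeds in between. At 3 months positive women are asked about a pap smear, so a missed result may surface then. If that call also fails, no later contact is scheduled.

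**Effect of an enquire-by date.** A date of 4 weeks is a proposal: analysis takes at most 2 weeks, contact is due by week 3, and 1 week is added as margin. A woman who acts on it would learn her result about 13 − 4 = 9 weeks before the 3-month call.

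The number of women affected cannot be calculated, because the protocol gives neither an HPV positivity rate nor a contact-failure rate.

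**The case against.** The strongest reply is that the protocol already places firm duties on the team. Every positive woman is to receive her result, to be contacted at 2-3 weeks and to be guided to a referral centre. A team that rang once and then stopped would not have met those duties. The number of attempts is operational detail that a working procedure can hold, and the safety plan and the information sheet are not available to check. The drop-in option comes after both the result call and the 3-month call in section 4.6, so it can be read as serving result delivery for women without a phone.

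Much of this stands. It makes failed contact less likely and limits how certain one can be about the gap. It does not answer the part that the protocol itself fixes, which is the message. However many attempts are made, a woman who is not reached has been told that only positives are called, and nothing stated prompts her to ask.

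Three stronger readings are tempting, and the documents do not support them.

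- *The study tells a positive woman that she is negative.* It tells her that a call comes only if she is positive. The negative conclusion is her own inference, although a natural one.
- *Missed women will wait 10-11 weeks.* A retry rule that is not stated does not mean that no retry will be made. The figure is what follows if none succeeds.
- *The trial's results are compromised, or Hypothesis 5.1 uses the wrong denominator.* The arm 3 primary endpoint is acceptance of the self-test on site, which is settled before any result exists. The protocol fixes no denominator for Hypothesis 5.1, so there is none to correct. The effect on that hypothesis is limited: the 3-month question on why no pap smear was taken can show failed notification, though only among women reached.

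**Conclusion.** The point holds as a participant-safety weakness in a stated procedure. Section 4.5.4 gives silence a meaning, and the protocol states neither a retry rule nor an enquire-by date for a positive-result contact that fails. The possible delay is up to 10-11 weeks from the planned contact. This takes 3 months as 13 weeks and assumes that no retry succeeds before the 3-month call. The delay is open-ended if that call fails too.

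Confidence is medium, because the safety plan may cover part of the gap. This is a cheap improvement to a participant-facing procedure and not a flaw in the trial's main comparison. It is also not a matter that a statistical analysis plan would settle.

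**What to change.** 1. In section 4.5.4 and the information sheet, replace the message with wording such as: *If you are positive we will contact you by your chosen route; if you have heard nothing by 4 weeks after sampling, contact this number.* The number must reach the community-based researcher who holds the link between code and name, because section 5.2.2.4 bars other team members from seeing names and contacts.
2. Apply at least the 5-attempt, multi-channel rule of section 5.2.2.4 to positive-result contacts.
3. Record notification status and date for each positive woman.

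The cost is one reworded message, one sentence on attempts, one status field with a date, and some enquiries from HPV-negative women. If the safety plan already sets a retry procedure, a cross-reference can replace item 2. The message should still change, because it gives an unreached woman no reason to enquire.
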